1.2.2 ARC002

All placebo subjects who completed ARC001 were eligible for rollover into the open-label ARC002 study. Placebo subjects in ARC002 underwent an escalation schedule identical to that for AR101 subjects in the ARC001 protocol. All subjects on AR101 who passed the DBPCFC by tolerating ≥ 443 mg cumulative of peanut protein with no more than mild symptoms were also eligible to enter ARC002.

Group 1 included subjects who completed the placebo arm of ARC001 and consented to enroll in ARC002, crossing over to active treatment using the same dosing regimen used in ARC001, but in open-label fashion. After completion of the buildup phase, Group 1 subjects underwent a DBPCFC (to a maximum single dose of 600 mg of peanut protein, or 1043 mg of cumulative peanut protein). Subjects who did not tolerate the post-low-dose buildup phase DBPCFC at ≥ 443 mg were considered escalation failures and were discontinued from the study for safety considerations. Those subjects who tolerated the DBPCFC at ≥ 443 mg of peanut protein entered an approximately 3-month (12- to 24-week) plateau phase of continued dosing at 300 mg/d. Group 2 subjects completed the active AR101 arm of ARC001 and consented to enroll directly into the 300 mg/d, 3-month plateau phase of ARC002. Following completion of the 3-month plateau phase, subjects underwent a post-plateau phase DBPCFC (to a maximum single dose of 1000 mg of peanut protein, or 2043 mg cumulative).

Based on the total population of 26 Group 1 subjects receiving ≥ 1 dose of AR101, 76.9% of subjects tolerated 300 mg and 65.4% tolerated 600 mg. At the post-plateau DBPCFC in 40 subjects in Groups 1 and 2, 100%, 90%, and 60% of the subjects tolerated a cumulative peanut protein dose of 443 mg, 1043 mg, and 2043 mg, respectively. These findings demonstrate the persistence of desensitization during daily maintenance treatment with AR101 at 300 mg/d, further supporting the primary endpoint selection in the ongoing phase 3 trial ARC003. They also indicate that treatment with AR101 may achieve a maximum tolerated dose of food allergen substantially higher than the dose used for maintenance itself.

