3.1.2 Up-dosing (Group 1 Only)

Subjects will receive AR101 starting at a dose of 3 mg once daily and gradually escalating every 2 weeks to a maximum of 300 mg once daily, according to the Up-dosing Maintenance

Schedule ([Table 2](#)). All escalation doses will be administered under direct observation; subsequent doses will be dispensed to the subject/guardian and administered at home. Doses may be adjusted for tolerability or intercurrent illness; the Up-dosing period may thereby be extended to a maximum of 40 weeks. Subjects unable to escalate to 300 mg within 40 weeks will be considered escalation failures for analysis purposes. Subjects able to escalate to 300 mg and maintain this dose regimen for 2 weeks will have completed Up-Dosing and will enter the Maintenance Period.

Table 2: Up-dosing Maintenance Schedule (Group 1 Subjects Only)

Up-dosing and Maintenance Schedule (Group 1 only)			
Dose Number	AR101 Dose, mg	Interval (weeks)	Percent Increase from previous dose
1	3	2 ^a	n/a
2	6	2	100
3	12	2	100
4	20	2	67
5	40	2	100
6	80	2	100
7	120	2	50
8	160	2	33
9	200	2	25
10	240	2	20
11	300	2	25

^a Interval includes Day 2 of Initial Escalation.

n/a = not applicable.

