Whenever this number is greater than 50%, then this stopping rule is met and further prolongation of the dosing interval in any subsequent cohort will cease. As an additional safety precaution, if individual stopping rules (eg, due to AEs) are invoked in 10 of the first 20 subjects to enroll in any cohort, further enrollment in that cohort will cease. Finally, the SMC retains the authority to stop further enrollment into a cohort at any time for any reason. If any of these conditions transpire, all remaining subjects, including those ongoing subjects in the terminated cohort, and future subjects, will be administered AR101 300 mg at the longest interval tolerated by a previous cohort.

*Assumptions = Up to approximately 500 ARC003 completers (having received active or placebo in ARC003 at a 3:1 ratio) are projected for recruitment into ARC004. This assumes a loss of 15% of the randomized ARC003 population due to attrition, AEs, etc. Thus, the planned sizes for the ARC004 cohorts is as follows, though the actual number may vary due to recruitment:

- Cohort 1 = 120, prespecified
- Cohort 2 = 50, prespecified
- Cohort 3 = 175, distributed equally across Cohorts 3A, 3B, 3C
- Group 1 = 130 (25% of ARC003 enrollment, accounting for 5% dropout)

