In OIT studies, gastrointestinal adverse events (GI AEs) are typically prominent (Anagnostou et al, 2014; Yu et al, 2012; Blumchen et al, 2010; Jones et al, 2009) and account for a substantial proportion of premature discontinuations of study treatment (Burks et al, 2012; Varshney et al, 2011; Jones et al, 2009; Vickery et al, 2011). This was also observed in the completed ARC001 study and the ongoing ARC002 study. In the ARC001 study, 6 out of 29 subjects (21%) receiving active treatment discontinued prematurely. Four of the early discontinuations were attributed by the Principal Investigators to have been the consequence of recurrent GI AEs; in 1 of these cases the diagnosis of EoE was subsequently established by endoscopic biopsy. In the other 3 discontinuations, ≥ 1 GI AE had occurred in each subject. In the ongoing ARC002 study, an open-label follow-on to the ARC001 study, 6 of the 26 subjects (22%) who had been assigned to the placebo group in ARC001 discontinued therapy prematurely. Four of these early discontinuations were due to recurrent GI AEs and 2 were due to study visit scheduling difficulties.

Repeated bouts of abdominal pain and vomiting are common to both EoE and chronic/recurrent OIT-related GI symptoms, suggesting a common, or at least a similar, etiology in at least a proportion of patients. To date, ≥ 20 occurrences of OIT-related GI AEs have been confirmed histopathologically to be EoE as reported in the medical literature (Hofmann et al, 2009; Vickery et al, 2011; Wasserman et al, 2011; Sánchez-García et al,

2012; Lucendo et al, 2014), and in still other cases the symptomatology and clinical course (with or without concomitant blood eosinophilia) have been highly suggestive of EoE (Narisety et al, 2009; Vickery et al, 2011). A recent review of the literature (Lucendo et al, 2014) has indicated that the incidence of confirmed EoE in OIT is on the order of 3% (ranging from approximately 1% to 5%), but the incidence of suspected EoE on clinical grounds may be in the vicinity of 15 to 25%.

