| BIW | Group 2, Cohorts 2, 3B, and 3C | The first day of AR101 therapy in study ARC004 while on BIW dosing | The last day of AR101 therapy in study ARC004 while on BIW dosing |
|-----|--------------------------------------|--------------------------------------------------------------------------|----------------------------------------------------------------------|

The total amount of study product consumed will be calculated as the sum of in-clinic doses plus the sum of doses taken at home as recorded in the diary.

The following calculations of study product exposure will be made and summarized:

- Duration of Exposure (in days and in months): calculated as the date of last dose of study product minus the date of the first dose of study product plus one during the study period. Duration of exposure will be summarized using descriptive statistics as well as categorically by the expected lengths of the overall treatment period.
- Total dose consumed (mg): calculated as the cumulative sum of all doses taken during the study period.
- Average dose per day (mg): calculated as the total dose consumed divided by the number of days during the study period.
- For Group 1 only: Maximum dose achieved (mg/day) during up-dosing using descriptive statistics for continuous data as well as categorically using all possible dose levels: 0.5, 1, 1.5, 3, 6, 12, 20, 40, 80, 120, 160, 200, 240, or 300 mg/day.
- For Group 1 only: Time to 300 mg dosing and time to 80 mg dosing for the overall treatment period using Kaplan-Meier methodology. Time will be calculated as date of the first 300 mg (or 80 mg) dose minus the first dose date +1. Subjects who do not reach the specified dose will be censored at the date of their last study product dose.

The non-missing valid diary entries will be used to estimate at-home dosing compliance. The following measures of compliance with at-home dosing will be calculated:

- Total number of planned at-home dosing days: calculated as the number of days where a valid diary entry was made, but excluding entries where a dose was missed because of doctor's orders.
- Percentage of planned dosing days where a full or partial dose was consumed.
- Percentage of planned dosing days where a full dose was consumed.
- Percentage of planned dosing days where a partial dose was consumed.
- Percentage of planned dosing days where a dose was missed.

Sponsor: Aimmune Therapeutics, Inc.

Protocol: ARC0004

Version: Version 1.0, 10Jul2019

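### Kaplan-Meier time to 300 mg and 80 mg in Group 1 censors subjects who stop AR101, so it overstates the share of treated subjects reaching the dose by a given week

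*SAP*

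**What the plan says.** For Group 1 only, SAP 10.1 (Study Treatment Exposure) lists "Time to 300 mg dosing and time to 80 mg dosing for the overall treatment period using Kaplan-Meier methodology". Time runs from the first dose to the first dose at the target level. The handling of everyone else is one sentence: "Subjects who do not reach the specified dose will be censored at the date of their last study product dose". The SAP mentions no competing event and no cumulative incidence.

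The protocol sets out why a Group 1 subject may stop before 300 mg:

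- 3 mg is not tolerated in initial escalation (3.1.1).
- Three consecutive escalation attempts fail (6.3.3.1, 7.8.2).
- Successively reduced doses are not tolerated (6.5.5.1.1).
- Epinephrine is needed for a third consecutive time in an escalation attempt (6.5.6).
- The time limit is reached. Protocol 3.1.2 says: "Subjects unable to escalate to 300 mg within 40 weeks will be considered escalation failures for analysis purposes".

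Two other planned summaries bear on this. The bullet just before the Kaplan-Meier one in SAP 10.1 tabulates the maximum dose achieved in up-dosing by category, with 80 and 300 mg/day among the categories. SAP 8.1 gives the number and percentage entering each study period.

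**The concern.** Kaplan-Meier censoring assumes that a censored subject would have gone on to reach the dose at the same rate as those still under observation. For a subject who has stopped AR101 that rate is zero, and in many cases stopping is itself the record of failed escalation. The estimate then answers a hypothetical question: how quickly would the dose be reached if nobody could stop? A reader of an exposure section wants the plainer one: of the placebo crossovers who started AR101, what share had reached the dose by a given week?

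Timing makes the problem sharper. Steps are two weeks long, so 300 mg (dose 11) is first possible at about week 20. Anyone who stops before then leaves the risk set before the first event and has no influence on the curve. The quantities at stake are the proportions by week and the median, which no other planned table supplies.

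**Working it through.** **Inputs from the documents.**

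- Planned Group 1 size is 130 (Protocol 7.8.3).
- Earliest week for 300 mg is 10 steps × 2 weeks = 20. For 80 mg (dose 6) it is 5 × 2 = 10 (Protocol 3.1.2, Table 2).
- The latest week is 40 (Protocol 3.1.2).
- Earlier discontinuation comes from Protocol Appendix 6, Background: "In the ARC001 study, 6 out of 29 subjects (21%) receiving active treatment discontinued prematurely" and "6 of the 26 subjects (22%) who had been assigned to the placebo group in ARC001 discontinued therapy prematurely".

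Reproducing those rates: 6/29 = 20.7%, which matches the printed 21%. 6/26 = 23.1%, against a printed 22%. Protocol 1.2.2 reports for the 26 ARC002 crossovers that "76.9% of subjects tolerated 300 mg and 65.4% tolerated 600 mg", and 20/26 = 76.9%.

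**Assumption.** A share of 20% never reaches 300 mg: 26 of 130, leaving R = 104 who do. The documents do not give this share for ARC004, so a range of 10% to 30% is shown below.

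**Formula.** Suppose *s* of the non-reachers are still dosing after the last subject reaches 300 mg, and the others stop before week 20. The risk set is then R + s when events begin, and nobody is censored while events occur. After *k* subjects have reached 300 mg:

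- one minus Kaplan-Meier = k / (R + s)
- share of treated subjects who have reached the dose = k / N
- ratio of the two = N / (R + s), the same at every week

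No assumption about the speed of escalation is needed. The middle column is the curve's value when 65 of 130 (50%) have actually reached 300 mg. The last column is the number of subjects at 300 mg when the curve first reaches 50%; the correct number is 65.

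| Non-reachers still dosing at week 40 (s) | Final curve (true 80.0%) | Curve when truth is 50% | Subjects at 300 mg when curve reaches 50% |
|---|---|---|---|
| 0 | 104/104 = 100% | 65/104 = 62.5% | 52 |
| 5 (a fifth) | 104/109 = 95.4% | 65/109 = 59.6% | 55 |
| 13 (half) | 104/117 = 88.9% | 65/117 = 55.6% | 59 |
| 26 (all) | 104/130 = 80.0% | 65/130 = 50.0% | 65 |

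**Range for the assumed share.** Final curve for none, about a fifth, about half, and all of the non-reachers still dosing at week 40:

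- 10% never reach (R = 117): 100%, 117/120 = 97.5%, 117/123 = 95.1%, 90.0%.
- 23.1% never reach (R = 100): 100%, 100/106 = 94.3%, 100/115 = 87.0%, 76.9%.
- 30% never reach (R = 91): 100%, 91/99 = 91.9%, 91/111 = 82.0%, 70.0%.

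**Stopping spread over time.** This case needs simulation: 300 data sets of 130, 20% never reaching, and an assumed exponential delay beyond week 20 (mean 4 weeks, two-week grid, capped at week 40). If stopping is uniform to week 30, the curve ends at 100%. If uniform to week 40, it ends at 96.9% on average. Under the same assumed delay, the median is about 22.6 weeks by Kaplan-Meier against 24.0 by cumulative incidence when all non-reachers stop before week 20, and 23.5 against 24.0 when half remain to week 40.

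**80 mg.** The same algebra applies from week 10. The share never reaching 80 mg cannot exceed the share never reaching 300 mg, but the documents give no figure for it.

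**The case against.** The strongest reply is that this is one descriptive bullet in an exposure section. Time to dose is not among the objectives or the primary or secondary endpoints, no formal comparison is planned (SAP 6.4), and no stopping or interval-lengthening rule uses it. The maximum-dose table gives the uncensored share reaching 80 and 300 mg, and because up-dosing is limited to 40 weeks, that is essentially the share by week 40. SAP 8.1 adds part of the same information. All of this stands. A reader might infer that the true proportion is hidden, or that the main feasibility result of up-dosing is wrong; the documents support neither.

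A reader might also infer that the curve must climb to about 100%. It need not. That follows only if nearly all non-reachers stop before the last subject reaches 300 mg. Subjects who run into the 40-week limit while still dosing are censored after essentially all events and hold the curve down; if every non-reacher were of that kind, there would be no bias. That is unlikely given the earlier stopping rules, but the documents do not give the mix.

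The figure of one in five is borrowed. The 6/29 and 6/26 are discontinuations for any reason. The ARC001 ones are placed only before the exit challenge, which followed a maintenance period, and two of the six in ARC002 were for visit scheduling. In ARC002, 20 tolerating 300 mg plus 6 discontinued makes 26, which is consistent with early failure, but the protocol does not say so. Nothing supports carrying one in five over to 80 mg.

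Finally, SAP 10.1 does not say whether a curve, quantiles or percentages will be shown, since the table layouts are in a separate document. The censoring rule affects any of these outputs, though the median moved by only about 1.4 weeks in the least favourable case simulated at 20%.

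**Conclusion.** The censoring rule is wrong for the question the summary appears to answer, and the importance is minor. The direction is certain whenever any subject stops before the last one reaches the dose: the proportion reaching it by a given week is overstated, and the median can only be shortened. The size is not certain. With 20% never reaching 300 mg, the final value lies between 80% (no bias) and 100% against a true 80%, depending on when non-reachers stop. The 20% is an assumption informed by earlier studies, and the table also assumes that no non-reacher stops while others are still arriving at 300 mg. For 80 mg only the direction can be stated. The error is confined to the curve, its proportions by week and its quantiles.

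**What to change.** In SAP 10.1, replace the Kaplan-Meier method and its censoring sentence with the cumulative incidence function (Aalen-Johansen) for time to 80 mg and time to 300 mg, counting discontinuation of AR101 before the target dose, including stopping at the 40-week limit, as a competing event. Beside it, report n (%) of all treated Group 1 subjects reaching 80 mg and 300 mg by week 22 (the scheduled length of up-dosing) and week 40 (its maximum). If a Kaplan-Meier curve is kept, label it as conditional on remaining on treatment.

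The cost is about one sentence in the SAP and the matching table layout. The estimator is nonparametric, so it fits the statement in SAP 6.2 that no modeling will be done, and it uses dates already collected. Because the final analysis follows completion of all subjects (SAP 1.3), there should be little or no genuine censoring, and the estimate at each week should then reduce to the simple proportion of treated subjects who have reached the dose. It would also agree with the maximum-dose table in the same section.

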5.4 Assessment of Compliance with Study Treatment and Monitoring

Families will document daily dosing and any reaction to at-home dosing by diary logs. Central monitoring of compliance will be performed by comparing returned unused study product against the daily dosing records. Families will be provided with 24-hour emergency contact information for the site.

Doses of study product lost or destroyed at home will also be recorded in the diary logs. All unused study product should be brought back to the clinic with each visit for reconciliation of remaining capsules/sachets.

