For any anaphylactic reactions that are missing severity, severe, the highest severity on the Muraro scale, will be imputed. For any allergic reactions that are missing severity, severe, the highest rating on the Consortium of Food Allergy Research (CoFAR) scale, will be imputed. For any other adverse events that are missing severity, severe, the highest rating on the Common Terminology Criteria for Adverse Events (CTCAE) scale, will be imputed.

No imputations will be made for other missing data, unless specified otherwise.

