At-home dosing data will be listed. Daily diary records, including date and time, whether a full or partial dose was consumed (or the dose was missed), reason for partial or missed dose will be listed.

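### The SAP's planned at-home dosing days are really days with a diary entry, so undocumented scheduled days drop out and compliance can be overstated; for QOD and BIW the direction of error is unknown

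*SAP*

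**What the plan says.** SAP 10.1 gives the data source: "The non-missing valid diary entries will be used to estimate at-home dosing compliance". The total of planned at-home dosing days is "calculated as the number of days where a valid diary entry was made", "but excluding entries where a dose was missed because of doctor's orders". Four percentages use that total: full or partial dose, full dose, partial dose, and "Percentage of planned dosing days where a dose was missed". SAP 7.6 adds no rule for blank diary days: "No imputations will be made for other missing data, unless specified otherwise".

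The same section computes the total amount consumed "as the sum of in-clinic doses plus the sum of doses taken at home as recorded in the diary", and divides the total dose by the number of days in the study period to get average dose per day.

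Protocol 5.4 describes a second source: "Central monitoring of compliance will be performed by comparing returned unused study product against the daily dosing records". The SAP compliance measures do not use it.

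Protocol 5.2 treats late doses differently by regimen. A daily dose more than 6 hours late is not made up. A nondaily dose more than 6 hours late is classed as missed and then given the following day. The SAP does not say how that pair of diary days is counted, or whether an entry on a QOD or BIW off-day counts as a planned day.

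**The concern.** The label promises a schedule-based denominator and the definition delivers a documentation-based one. A day on which the subject neither dosed nor wrote anything is invisible to all four percentages, including the one for missed doses: a miss counts only if someone recorded it. Yet the same blank day contributes 0 mg to total dose and stays in the divisor for average daily dose, so two summaries in one section can give different pictures of the same subject.

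What is at stake is interpretation. Protocol 1.3 cites adherence as part of the rationale for longer intervals and asks whether intermittent dosing preserves desensitization. To read a cohort's exit challenge and adverse event results as results of its regimen, one needs to know how far the regimen was followed. For nondaily dosing the denominator has no link to the dosing calendar at all.

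**Working it through.** The documents give no compliance figure, diary completion rate or compliance threshold, so there is no figure of the plan's own to reproduce. The diary inputs below are assumptions. The schedule lengths come from SAP 2.3. Clinic days and ordered holds are ignored for simplicity.

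**General form.** Let d be the share of scheduled days documented, and c and u the compliance on documented and undocumented days.

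- SAP measure = c
- Scheduled-day compliance = d·c + (1−d)·u
- Difference = (1−d)(c−u)

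The difference is positive only if u < c, zero if u = c, and negative if u > c.

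**One QD subject, 28 weeks = 196 days.** Assume 150 doses logged, 5 misses logged, 41 days blank.

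- SAP: 150/(150+5) = 150/155 = 96.8%
- All blanks missed: 150/196 = 76.5%
- All blanks taken: (150+41)/196 = 191/196 = 97.4%
- Average dose per day, using the diary sum in SAP 10.1: 150×300/196 = 229.6 mg, which is 76.5% of 300 mg

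**Range over d and u.** Assume c = 95%, so the SAP measure reads 95% in every row. Documented days are rounded to 176, 157 and 137 of 196. Cells show scheduled-day compliance.

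| d | u = 0 | u = 50% | u = 95% | u = 100% |
|---|---|---|---|---|
| 90% | 85.3% | 90.4% | 95.0% | 95.5% |
| 80% | 76.1% | 86.0% | 95.0% | 96.0% |
| 70% | 66.4% | 81.5% | 95.0% | 96.5% |

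The overstatement at u = 0 is 9.7, 18.9 and 28.6 points. At u = 100% the SAP measure is too low by 0.5, 1.0 and 1.5 points.

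**Do blank days act differently by regimen?** QD with 98 of 196 doses taken and logged and the rest blank and missed: SAP 98/98 = 100%, scheduled 98/196 = 50%. BIW with 24 of 48 on the same terms: SAP 24/24 = 100%, scheduled 24/48 = 50%. The mechanism is the same.

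**What is specific to nondaily dosing.** BIW for 24 weeks is 48 doses in 168 days, leaving 120 off-days. QOD for 4 weeks is 14 doses in 28 days, leaving 14 off-days. Assume every dose is taken.

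- A fraction f of BIW off-days carries an entry that counts as planned: 48/(48+120f). For f = 0, 10, 25, 50 and 100% this gives 100, 80.0, 61.5, 44.4 and 28.6%.
- The same for QOD: 14/(14+14f). For f = 0, 25, 50 and 100% this gives 100, 80.0, 66.7 and 50.0%.
- m late BIW doses logged as missed and then taken the next day: 48/(48+m). For m = 2, 5 and 10 this gives 96.0, 90.6 and 82.8%.

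These effects understate compliance, opposite to the blank-day effect when u < c.

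**The case against.** A reader might infer that the rule does overstate compliance, and most where adherence is worst. The documents do not establish that. Protocol 5.2 directs subjects to document the product they take, which makes a blank day somewhat more likely to be a missed dose. But the diary also has a missed-dose option, and no completion rate is given. The direction depends on u, which is unknown.

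A reader might also infer that blank days alone make daily and nondaily compliance non-comparable. They do not, unless diary completion differs by regimen. The 28.6% BIW case is the extreme of a reading that the SAP neither adopts nor excludes, and an off-day fits poorly with diary categories of full, partial or missed dose.

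Other safeguards exist:

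- Average dose per day exposes the shortfall, and the count of diary-entry days can be read beside duration of exposure. One caveat is that SAP 10.1 opens by basing exposure on clinic dosing and the dispensed dose level; the cross-check relies on the later, more specific diary-sum sentence.
- Diary records are listed, and study drug compliance is a deviation category (SAP 5).
- On QD, 7 or more consecutive days missed through non-compliance, or 3 or more on 3 occasions, is a stopping rule (Protocol 7.8.2).
- Regimen periods end at the last dose on that regimen, so time after permanent stopping is not at issue.
- Compliance is not an endpoint (SAP 3), does not define either analysis population (SAP 4), and no formal comparisons are planned (SAP 6.4).

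These points stand and limit the consequence. They curb long silent gaps but not scattered ones, and none of them makes the percentage measure planned days.

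**Conclusion.** The denominator is mislabelled, and undocumented scheduled days drop out of all four percentages. Compliance can therefore be overstated by (1−d)(c−u), and is overstated whenever dosing is worse on undocumented days. In the illustration the reported 96.8% sits inside a range of 76.5% to 97.4%. The room for error is about 20 points downward and under 1 point upward, but where the truth lies depends on unrecorded behaviour, and the 41 blank days are assumed.

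For QOD and BIW the lack of a schedule link adds errors in the opposite direction, so the net direction is unknown. A claim that nondaily compliance is inflated relative to daily would go beyond the documents.

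This affects a descriptive exposure summary. It is worth correcting because that summary is used to judge whether each regimen was followed, and the change is inexpensive.

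**What to change.** Amend SAP 10.1 as follows.

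- Derive planned at-home dosing days from the assigned regimen and the first and last dose dates of each regimen period, allowing for intervals reset under Protocol 6.5.7. Subtract in-clinic and DBPCFC days and doctor-ordered holds.
- Report full, partial, missed and undocumented days as shares of that total.
- Give two bounds: undocumented days all missed, and undocumented days all taken.
- Treat an off-day entry as not planned. Count a next-day dose as one late dose against one scheduled dose.
- Cross-check against returned product where those counts are in the database. Protocol 5.4 describes the reconciliation, but the documents do not say the counts are available for analysis, and half-doses with the remainder discarded (Protocol 6.5.7) complicate them.

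The main items use regimen, date and diary data already collected. The cost is some derivation work, chiefly for reset nondaily intervals, and a less favourable lower bound, because doses taken but not recorded will show as undocumented.
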